3.2 SELECTION OF PROGRAM POPULATION

3.2.1 Main diagnosis for program entry

Participation in this program will be available to patients with GPP who meet the eligibility requirements specified in section [3.2.2](#) and section [3.2.3](#). Owing to the nature and objectives of this program, no recruitment goals or limits apply.

Patients previously enrolled in this program presenting with a new episode of a GPP flare must be re-evaluated and meet eligibility criteria to receive new treatment with spesolimab.

Please refer to section [8.3.1](#) (Source Documents) for the documentation requirements pertaining to the in- and exclusion criteria.

3.2.2 Inclusion criteria

1. Diagnosis of GPP, consistent with ERASPEN criteria, defined as primary, sterile, macroscopically visible pustules on non-acral skin (excluding cases where pustulation is restricted to psoriatic plaques). GPP can occur with or without systemic inflammation, with or without plaque-type psoriasis, and be either relapsing (>1 episode) or persistent (>3 months).
2. Patient is experiencing a flare, defined as new or worsening of widespread eruption of sterile macroscopically visible pustules, with or without systemic inflammation, as assessed by the treating physician.
3. Male or female patients, aged 18 to 75 years at time of enrolment. Women of childbearing potential (WOCBP)¹ must be willing and able to use a highly effective method of birth control per ICH M3 (R2) that result in a low failure rate of less than 1% per year when used consistently and correctly. A list of contraception methods meeting these criteria is provided in the patient information.
4. Signed and dated written informed consent in accordance with ICH-GCP and local legislation prior to admission to the program.
5. No satisfactory authorized alternative therapy exists, as assessed by the treating physician.

3.2.3 Exclusion criteria

1. Women who are pregnant, nursing, or who plan to become pregnant while in the program.
 - a) Women who stop nursing before study drug administration do not need to be excluded from participating; they should refrain from breastfeeding for 16 weeks after the last spesolimab [REDACTED].
2. Severe, progressive, or uncontrolled hepatic disease, defined as >3-fold Upper Limit of Normal (ULN) elevation in AST or ALT or alkaline phosphatase, or >2-fold ULN elevation in total bilirubin.
3. Active systemic infections (fungal and bacterial disease) during the last 2 weeks prior to drug administration, as assessed by the treating physician.
4. Increased risk of infectious complications (e.g. recent pyogenic infection, any congenital or acquired immunodeficiency (e.g. HIV), past organ or stem cell transplantation), as assessed by the treating physician.
5. Relevant chronic or acute infections, including active tuberculosis (TB), HIV infection or viral hepatitis at the time of drug administration.
 - a) Patients should be evaluated for TB infection prior to initiating treatment with spesolimab.

¹A woman is considered of childbearing potential (WOCBP), i.e. fertile, following menarche and until becoming post-menopausal unless permanently sterile.

Permanent sterilisation methods include hysterectomy, bilateral salpingectomy and bilateral oophorectomy.

Tubal ligation is NOT a method of permanent sterilisation.

A postmenopausal state is defined as no menses for 12 months without an alternative medical cause.

b) Anti-TB therapy should be considered, in accordance with local guidelines, prior to initiating spesolimab in patients with latent TB or a history of TB.

6. History of allergy / hypersensitivity to systemically administered spesolimab or its excipients.

7. Any documented active or suspected malignancy or history of malignancy within 5 years prior to screening, except appropriately treated basal or squamous cell carcinoma of the skin or in situ carcinoma of uterine cervix.

8. Immediate life-threatening flare of GPP requiring intensive care treatment according to the investigator's judgement. Life-threatening complications include cardiovascular / cytokine driven shock, pulmonary distress syndrome, or renal failure.

9. Patients who must or wish to continue the intake of restricted medications (other IL-36R inhibitors, live vaccinations, or IL-1R/IL-1 inhibitors, see section [4.2.2.1](#)) or any drug considered, in the judgement of the treating physician, likely to interfere with the safe conduct of the program.

10. Currently enrolled in another investigational device or drug program, or less than 30 days since ending another investigational device or drug program(s), or receiving other investigational treatment(s), or eligible to participate or participating in an ongoing actively accruing clinical trial with spesolimab in the treatment of GPP.

11. A disease or condition that in the opinion of treating physician may put the patient at risk because of participation in this program or limit the patient's ability to participate in this program.

12. Presence of acute demyelinating neuropathy.

3.2.4 Discontinuation / withdrawal of patients from program

Patients may discontinue program treatment or withdraw consent to program participation for any reason. The decision to withdraw consent to program participation and the reason must be documented in the patient files and CRF. If the reason for discontinuation is death, this should be reported on the SAE form as well, regardless of causal relationship.

3.2.4.1 Discontinuation of trial medication and assessment

An individual patient will discontinue treatment if:

- The patient wants to discontinue treatment. The patient will be asked to explain the reasons but has the right to refuse to answer.
- The patient has repeatedly shown to be non-compliant with important program procedures and, in the opinion of both the investigator and sponsor representative, the safety of the patient cannot be guaranteed as he / she is not willing or able to adhere to the program requirements in the future.
- The patient needs to take concomitant medication that interferes with the safety of the investigational medicinal product.
- The patient can no longer receive treatment for medical reasons such as surgery, adverse events, other diseases, or pregnancy.
- If a hepatic injury alert (as defined in Section [5.2.4.1.4](#)) is detected without identification of an alternative cause in the work-up according to the "DILI checklist", the patient should not receive subsequent doses of investigational medication. (If alternative cause is

Proprietary confidential information © 2022 Boehringer Ingelheim International GmbH or one or more of its affiliated companies

identified and patient has recovered according to investigator assessment, treatment can be restarted after consultation with the sponsor.)

- If peripheral neuropathy is suspected, treatment with spesolimab should be temporarily discontinued until a full neurological investigation has been conducted.
- After completion of the neurological investigation, treatment can be restarted based on medical judgement of the investigator.
- For individual stopping rules related to specific adverse events, please see Section [4.2.1](#) “Other treatments and emergency procedures.”

If new efficacy / safety information becomes available, Boehringer Ingelheim will review the benefit-risk-assessment and, if needed, pause or discontinue the [REDACTED]/treatment for all patients or take any other appropriate action to guarantee the safety of the patients participating in the program.

If a patient wants to discontinue the participation in the program, the investigator should request that the patient consent to be contacted, at least by phone, for a final follow-up assessment at 16 weeks after last drug intake. Where possible, any new or changes in previously reported AEs and concomitant therapies should be recorded at this assessment, as indicated in section [6.1.3](#). Specific information to be collected at the [REDACTED]-week assessment in patients who have discontinued triam medication or assessment is detailed in section [5.2.4.2.1](#).

3.2.4.2 Withdrawal of consent to program participation

Patients may withdraw their consent to program participation at any time without the need to justify the decision.

If a patient wants to withdraw consent, the investigator should be involved in the discussion with the patient and explain the difference between treatment discontinuation and withdrawal of consent to program participation, as well as explain the options for continued follow-up after treatment discontinuation, please see Section [3.2.4.1](#) above. This discussion, as well as the patient’s decision, should be well documented in the source.

3.2.4.3 Discontinuation of the program by the sponsor

Boehringer Ingelheim reserves the right to discontinue the program overall or at a particular site at any time for the following reasons:

1. New efficacy or safety information invalidating the earlier positive benefit-risk assessment.
2. Violation of GCP, the program protocol, or the contract impairing the appropriate conduct of the program.
3. Commercial availability of spesolimab i.v. or 6 months after marketing authorization in China, whichever is earlier.

The investigator / the program site will be reimbursed for reasonable expenses incurred in case of program termination (except in case of the second reason).

4. TREATMENTS

4.1 INVESTIGATIONAL TREATMENTS

4.1.1 Identity of the Investigational Medicinal Product

All patients will be treated with spesolimab in this program. There is no active comparator or placebo.

Table 4.1.1: 1 Spesolimab

Substance:	Spesolimab (BI 655130)
Pharmaceutical formulation:	Solution [REDACTED]
Source:	Boehringer Ingelheim Pharma GmbH & Co KG
Unit strength:	Spesolimab [REDACTED] [REDACTED]
Posology:	[REDACTED]
Method and route of administration:	[REDACTED]

4.1.2 Packaging, labelling, and re-supply

The investigational medicinal products will be provided by BI or a designated CRO. They will be packaged and labelled in accordance with the principles of Good Manufacturing Practice (GMP). Shipment of material to the local depots and/or sites will be managed via an IRT system, which will also monitor expiry dates of available supplies.

An Interactive Response Technology (IRT) system will be used to screen eligible patients, assign medication kits, and manage re-supply ordering of medication kits. At program entry, as well as subsequent medication administration visits (if applicable), and IRT system will assign medication numbers. Site personnel will enter the medication numbers in the eCRF. Note that the patient number is different from the medication number (the former is generated during screening via the IRT System). Each medication kit (containing 2 vials) will have a unique medication number.

For details of packaging and the description of the label, refer to the ISF.

4.1.3 Storage conditions

Drug supplies will be kept in their original packaging and in a secure limited access storage area according to the recommended storage conditions on the medication label. A

temperature log must be maintained for documentation. Program medication must be securely stored, e.g. in a locked refrigerator or at a pharmacy. If the storage conditions are found to be outside the specified range, the Clinical Research Associate (CRA) (as provided in the list of contacts) must be contacted immediately. Refer to the ISF for additional information.

The program medication must be administered in the manner specified in the EAP Protocol and instructions for IMP preparation handling and administration of spesolimab.

4.1.4 Drug accountability

The investigator or designee will receive the investigational drugs delivered by the sponsor when the following requirements are fulfilled:

- Approval of the clinical program protocol by the IRB / ethics committee.
- Availability of a signed and dated clinical program contract between the sponsor and the investigational site.
- Approval/notification of the regulatory authority, e.g. competent authority.
- Availability of the curriculum vitae of the Principal Investigator.
- Availability of a signed and dated clinical program protocol.
- Availability of the proof of a medical licence for the Principal Investigator.

Investigational drugs are not allowed to be used outside the context of this protocol. They must not be forwarded to other investigators or clinics.

All unused program medication must be returned to the sponsor. All used and partially used medication must be destroyed locally by the participating site. Receipt, usage and return or disposal must be documented on the respective forms. Account must be given for any discrepancies.

The investigator or designee must maintain records of the product's delivery to the participating site, the inventory at the site, the use by each patient, and the return to the sponsor or warehouse / drug distribution centre or alternative disposal of unused products. If applicable, the sponsor or warehouse / drug distribution centre will maintain records of the disposal.

These records will include dates, quantities, batch / serial numbers, expiry ('use-by') dates, and the unique code numbers assigned to the investigational medicinal product and patients participating in the program. The investigator or designee will maintain records that document adequately that the patients were provided the doses specified by the EAP Protocol and reconcile all investigational medicinal products received from the sponsor. At the time of return to the sponsor or appointed CRO, the investigator or designee must verify that all unused drug supplies have been returned by the clinical staff and all used or partially used supplies have been destroyed by the participating site, and that no remaining supplies are in the investigator's possession.

4.2 OTHER TREATMENTS, EMERGENCY PROCEDURES, RESTRICTIONS

4.2.1 Other treatments and emergency procedures

All concomitant therapies will be recorded on the appropriate pages of the electronic CRF (eCRF).

4.2.1.1 Emergency procedures

Systemic hypersensitivity including [REDACTED] reactions and anaphylactic reaction

In case of systemic hypersensitivity, including [REDACTED] reactions and anaphylactic reaction, emerging during or after [REDACTED] of investigational medication, the investigator should consider, in accordance with severity of the reaction and local standard of care, to:

- Immediately interrupt the [REDACTED]
- Treat with systemic antihistamines, i.v. steroids, and in case of a severe allergic reaction (e.g., anaphylactic reaction) epinephrine
- Refer the patient to an emergency unit

In case of systemic hypersensitivity including [REDACTED] reactions, based on the patient's clinical course and the physician's medical judgment, the [REDACTED] may be re-initiated in case of mild or moderate systemic hypersensitivity, including [REDACTED] reactions (according to NCI grading, grade 1 or 2), at a slower speed with a gradual increase to complete the [REDACTED] as detailed in the Instructions for Preparation and Handling of spesolimab in the ISF. [REDACTED]
[REDACTED]

In case of anaphylactic reactions based on published criteria (Appendix [10.1](#); [R11-4890](#)), the investigator should discontinue treatment with spesolimab.

When a delayed hypersensitivity reaction is suspected, in addition to drawing a blood sample for laboratory assessment (complete blood count with differential, comprehensive metabolic panel (includes liver enzymes), LDH, immune complexes profile), please evaluate for signs of extra-cutaneous organ involvement. The decision to discontinue treatment and/or restart treatment after resolution of the reaction should be based on reaction type and severity.

In case of potential systemic allergic reaction: where possible, blood samples for determination of serum tryptase, as well as histamine, IgE and serum complement component assay, should be collected 0.5 h, 2 h, 6 h, 24 h after onset of the event.

Any clinically meaningful changes in laboratory values should be reported as an AE, SAE or AESI (as appropriate).

Severe infections (according to RCTC grading the ISF), serious infections, opportunistic or mycobacterium tuberculosis infections

Treatment of the infection should be initiated promptly according to local standard of care.

Active/Latent TB:

A suitable TB test, according to local regulations will be performed at screening. If the result is positive, the patient may participate in the program if further work up (according to local practice/guidelines) establishes conclusively that the patient has no evidence of active tuberculosis. Active TB patients must be excluded. If the presence of latent tuberculosis is established, then treatment should have been initiated and maintained according to local country guidelines. If the TB test results are not available at the time of [REDACTED], these patients may receive treatment (provided they meet all other inclusion/exclusion criteria) as long as the investigator has ruled out active disease based on available documented history (i.e. negative for active TB) within 3 months prior to [REDACTED].

Malignancies

In case of occurrence of malignant neoplasm other than appropriately treated basal cell carcinoma or squamous cell carcinoma of the skin or in situ carcinoma of uterine cervix, treatment discontinuation is to be a consideration if deemed clinically appropriate by the investigator. In addition, diagnostics and treatment are to be initiated according to local standard of care.

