Malignancies	
Inhibition of the immune response with an immunomodulatory drug may potentially impair immune defences and thus theoretically decrease immune defence against malignancies.
 
A recent characterisation of individuals with homozygous IL36R KO mutations revealed that normal immune function was broadly preserved, suggesting that IL36 signalling pathway inhibition does not compromise host defences [R17-3632].
	
Patients with a recent (within 5 years) history of malignancy will be excluded from participation in this program except appropriately treated basal or squamous cell carcinoma of the skin or in situ carcinoma of uterine cervix.
 
In case of occurrence of malignant neoplasm, other than appropriately treated basal cell carcinoma or squamous cell carcinoma of the skin or in situ carcinoma of uterine cervix, the investigator should discontinue treatment with spesolimab.
 
Diagnostics and treatment will be initiated according to local standard of care.
 
Malignancies always represent SAEs and are subject to close monitoring.

Peripheral Neuropathy	
Three cases reported by the investigator as Guillain-Barré syndrome (GBS) were received in ongoing clinical trials with spesolimab. A panel of independent neurologists and experts in the study of neuropathies assessed the 3 cases. Only 1 met level 4 diagnostic certainty for the diagnosis of GBS (lowest level on Brighton scale of 1 to 4). In that case, there was a coincident infection with SARS-CoV-2. The other 2 cases were assessed as not GBS. Observed cases
	
Timely detection, evaluation, and follow-up of suspected peripheral neuropathies to ensure patients' safety.
 
Use of dedicated questions to elicit neurologic history during screening and exclusion criteria to avoid selection of patients with acute demyelinating neuropathy.
 
Targeted Follow up questions to gather detailed information in case of any event during trial to ensure proper decision making.

Table 1.4: 1

Risks associated with spesolimab administration (cont.)

Risks of clinical relevance for this trial	Summary of data, rationale for the risk	Mitigation strategy
	showed a heterogenous pattern. As per assessment by the panel of external neurologists the nonspecific symptoms and findings in all three cases may best be referred to as peripheral neuropathy.	Trial treatment discontinuation criteria as well as criteria for trial treatment restart are implemented for relevant cases.

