3. DESCRIPTION OF DESIGN AND PROGRAM POPULATION

3.1 OVERALL PROGRAM DESIGN AND PLAN

This is an open-label, multi-centre, single-arm trial, designed to provide early access to spesolimab, for patients with GPP presenting with a flare and for whom no satisfactory authorised alternative therapy exists and who are unable to participate in a clinical trial, as assessed by the treating physician.

After signing informed consent and if all eligibility criteria are met, patients will receive a [REDACTED] spesolimab. If deemed necessary by the treating physician (i.e. if the flare symptoms persist), a [REDACTED] spesolimab may be administered [REDACTED] after the initial [REDACTED].

If [REDACTED] is administered, then patients will visit the treating physician approximately at week [REDACTED], week [REDACTED] and week [REDACTED]. If a [REDACTED] may be given, then the dates that patients will visit the treating physician is changed to approximately at [REDACTED] [REDACTED] after initial dose of spesolimab. Please refer to section [6.1](#) for details on the program visit procedures. Patient's participation in the program will end after conclusion of the [REDACTED]-week follow-up period after the last [REDACTED] / drug administration.

If a patient experiences a new GPP flare (following the resolution of a previous flare with spesolimab treatment) after the [REDACTED]-week follow-up period the patient may re-enter in the program and be treated again with spesolimab, providing eligibility criteria are still met and the overall program is still running. The same dosing and follow-up requirements apply as for the previous flare.

In the situation that a patient experiences a new GPP flare within the [REDACTED]-week follow-up period and the physician wishes to treat this new flare with spesolimab, eligibility needs to be assessed and agreed upon with the BI clinical team.

The enrolment of patients for the program will stop at the time spesolimab becomes commercially available or 6 months after marketing authorization for treatment of GPP in China (whichever is earlier). The overall program will close when the last patient completes the follow up period after the last [REDACTED] of spesolimab or if any other reason listed in section [3.2.4.3](#) is met.

Below is suggested flow chart for patient visit.

Flow Chart

Trial Period	Screening	Treatment		Follow-up Period		
Visit	V1 ¹	V2 ¹	V3 ²	V4	V5	V6/EoS ³
Week [REDACTED]) ²						
Week [REDACTED]) ²						

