Window			±1d	±1d	±7d	±7d
Informed consent	X					
Demographics	X					
Medical history	X					

Proprietary confidential information © 2022 Boehringer Ingelheim International GmbH or one or more of its affiliated companies

Trial Period	Screening		Treatment		Follow-up Period	
	V1 ¹	V2 ¹	V3 ²	V4	V5	V6/EoS ³
Visit						
Week [REDACTED] ²						
Week [REDACTED] ²						
Window			±1d	±1d	±7d	±7d
Baseline condition	X					
Physical examination	X	X	(X) ⁵	(X) ⁵	(X) ⁵	(X) ⁵
Vital signs	X	X	(X) ⁵	(X) ⁵	(X) ⁵	(X) ⁵
Pregnancy test ⁴	X					
Infection testing ⁶	X					
Safety laboratory tests (Local lab) ⁷	X		(X) ⁵	(X) ⁵	(X) ⁵	(X) ⁵
Nucleic acid testing	X					
COVID-19 symptoms		(X)	(X)	(X)	(X)	(X)
Review of in-/exclusion criteria	X	X				
IRT transaction	X	X	X			
Dispense/administration study drug		X	X			
Adverse events	X	X	X	X	X	X
Concomitant therapy	X	X	X	X	X	X
[REDACTED]						
Study Completion						X

Abbreviations: EoS: end of study; IRT: Interactive Response Technology; V: Visit.

- 1: Visit 1 and Visit 2 can be on the same day. If V1 and V2 is performed on the same day, the procedures do not need to be repeated.
- 2: V3 is an additional visit. There's a possibility that patient will receive [REDACTED] of spesolimab at V3 [REDACTED] if his flare symptoms persist after the [REDACTED] dose. If in that case, the visit schedule will be changed to approximately at [REDACTED] after initial dose of spesolimab.
- 3: Should a patient prematurely discontinue from the treatment; every effort should be made to keep the patient in the trial and complete all of the remaining study visits. If a patient is not willing to follow the whole visit schedule, the EOS Visit (Visit 6) should be conducted at [REDACTED] weeks after the last spesolimab administration at a minimum. If patients refuse to return to the study site, early EoS visit should be completed at the timing of prematurely discontinuation and then at least safety information should be collected by phone at [REDACTED] weeks after the last spesolimab administration.
- 4: Only applicable for women of childbearing potential.
- 5: Physical examination, vital signs and safety laboratory test shown with parentheses "(X)" are optional and will be performed according to standard clinical practice and when deemed appropriate by the investigator.

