These include pneumocystis jirovecii, BK virus disease including PVAN, CMV, posttransplant lymphoproliferative disorder (EBV), progressive multifocal leucoencephalopathy, bartonellosis (disseminated only), blastomycosis, toxoplasmosis, coccidioidomycosis, histoplasmosis, aspergillosis (invasive only), candidiasis (invasive or pharyngeal), cryptococcosis, other invasive fungi (mucormycosis (zygomycosis, rhizopus, mucor, lichtheimia), scedosporium/pseudallescheria boydii, fusarium), legionellosis, listeria monocytogenes (invasive only), tuberculosis, nocardiosis, non-tuberculous mycobacterium, salmonellosis (invasive only), HBV reactivation, herpes simplex (invasive only), herpes zoster, strongyloides (hyperinfection syndrome and disseminated forms only), paracoccidioides, penicillium marneffei, sporothrix schenckii, cryptosporidium species (chronic only), microsporidiosis, leishmaniasis (visceral only), trypanosoma cruzi infection (Chagas' disease) (disseminated only), campylobacteriosis (invasive only), shigellosis (invasive only), vibriosis (invasive due to vibrio vulnificus), HCV progression ([R17-2617](#)).

Peripheral neuropathy

Any event suspected or diagnosed as Peripheral Neuropathy is considered as an AESI. For the treatment interruption rules, please see section [1.4](#) and [3.2.4.1](#).

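### The benefit-risk table says spesolimab should be stopped after a new malignancy, but the stopping rule in Protocol Section 4.2.1.1 makes this optional

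*Protocol*

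**What the plan says.** Two current, unredacted texts in the protocol tell the investigator what to do when a malignancy occurs during the program.

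- **Section 1.4, Table 1.4: 1, Malignancies row, mitigation column:** "the investigator should discontinue treatment with spesolimab".
- **Section 4.2.1.1, Malignancies paragraph:** "treatment discontinuation is to be a consideration if deemed clinically appropriate by the investigator".

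Both exempt treated basal cell and squamous cell skin cancers and in situ cervical cancer.

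Section 3.2.4.1, which lists when a patient stops treatment, does not name malignancy. It has a general rule, "The patient can no longer receive treatment for medical reasons such as surgery, adverse events, other diseases, or pregnancy", and then a pointer: "For individual stopping rules related to specific adverse events, please see Section" 4.2.1. The amendment description in Section 11 mentions neither malignancy text.

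**The concern.** A benefit-risk table tells ethics committees and regulators how each risk will be contained. Here it presents stopping the drug as the response to a new malignancy. The rule that a site reaches by following the protocol's own pointer asks only that stopping be considered. Two sites facing the same event could act differently and each point to the protocol in support. At stake is whether a patient in whom a cancer has just been found receives another dose of an immunomodulatory antibody, when a merely suspected cancer would have kept that patient out at entry.

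**Working it through.** No sample size, power or error rate is involved, so the check is a comparison of texts followed by a count of the doses that the weaker wording could allow.

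**1. Same event, different strength.** The triggering event and the exceptions match in Table 1.4: 1 and Section 4.2.1.1. Only the instruction differs: a recommendation to stop against an option to stop.

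**2. Whether the difference in strength is meant.** Section 4.2.1.1 uses both levels itself. For systemic hypersensitivity in general, the investigator should consider a set of measures. For anaphylaxis the instruction is to discontinue, in the same words that Table 1.4: 1 uses for malignancy. Within this protocol, considering and discontinuing are distinct instructions.

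**3. Which text operates.** Section 3.2.4.1 sends the reader to Section 4.2.1 for rules tied to specific adverse events. The discretionary text is therefore the operative one, and the table describes a firmer measure than that text applies.

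**4. Doses left after a new malignancy.**

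- *Current flare.* The flow chart in Section 3.1 marks "Dispense/administration study drug" at V2 and V3. V3 is the optional further dose for persisting symptoms, so at most 2 − 1 = 1 dose remains after the first. The row "Review of in-/exclusion criteria" is marked at V1 and V2 only, so exclusion criterion 7 is not scheduled for re-checking before V3. The chart is introduced as a suggestion ("Below is suggested flow chart for patient visit").
- *Later flares.* Sections 3.1, 3.2.1 and 6.1.3 require eligibility to be met again, and a flare within the follow-up period also needs the sponsor's agreement. Exclusion criterion 7 bars active or suspected malignancy and any history within 5 years, with the same exceptions. Doses allowed in that time: 0.

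**5. Length of the exposed window.** The interval between doses is redacted in the protocol. SAP Section 7.8.5 summarises local tolerability at Day 1 and Day 8. If V3 is Day 8 (an assumption), the window is 8 − 1 = 7 days. With the ±1 day visit window at V3 it is 7 − 1 = 6 to 7 + 1 = 8 days. This is a length of time, not an event rate. The documents give no malignancy rate from which an expected number of cases could be worked out.

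**6. Effect on the analysis.** The primary and secondary endpoints (Protocol Sections 2.1.2 and 2.1.3; SAP Section 7.8.1) count the occurrence of treatment-emergent AEs, SAEs and AESIs. A malignancy counts as an AE and an SAE whether or not the drug is stopped.

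**The case against.** The strongest reply is that the conflict is one of degree and the safeguards around it leave almost nothing exposed. An investigator who stops complies with both texts. The V3 dose is given only if the treating physician judges it necessary. Adverse events are recorded at V3 even though eligibility is not reviewed there. Cancers must be classed as serious (Section 5.2.4.1.3), and SAEs go to the sponsor within 24 hours of awareness (Section 5.2.4.2.2). The general medical-reasons rule in Section 3.2.4.1 already allows stopping. Discretion can also be defended for a potentially life-threatening flare in patients without a satisfactory alternative.

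All of this stands as a limit on the consequence. It does not remove the mismatch. The general rule does not say that a malignancy meets its condition, and none of these safeguards turns the option to stop into the recommendation that the table states.

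A reader might infer more than the documents support in two ways.

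- *That the protocol leaves open which text governs.* Support might be sought in Section 5.2.4.1.4, which says for peripheral neuropathy "For the treatment interruption rules, please see section" 1.4. That sentence also names Section 3.2.4.1, where the neuropathy rule actually stands. The neuropathy row of Table 1.4: 1 contains no stopping rule and says only that such criteria are in place. The cross-reference does not make the table a competing source of stopping rules, and Section 3.2.4.1 settles the matter for malignancy by pointing to Section 4.2.1.
- *That a patient with a new cancer could be re-treated flare after flare.* Exclusion criterion 7 applies again at every re-entry, so this does not follow.

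**Conclusion.** The inconsistency is real: the operative stopping rule does not deliver the mitigation on which the benefit-risk assessment relies. Confidence is high for the textual mismatch, which rests on two complete, current sentences. The size is very small: at most one optional dose, in the current flare only, after a non-exempt malignancy found between two doses and followed by a physician's decision to dose anyway. The window of about 7 days (6 to 8) holds only if V3 is Day 8; the SAP does not call Day 8 a dosing day, and it covers three trials. Severity is minor. This is an internal inconsistency in a safety rule, not a design choice and not a threat to the endpoints.

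**What to change.** In the Malignancies paragraph of Section 4.2.1.1, replace "treatment discontinuation is to be a consideration if deemed clinically appropriate by the investigator" with "the investigator should discontinue treatment with spesolimab". This carries the mitigation from Table 1.4: 1 into the rule that sites follow. It covers the V3 dose directly, so no added eligibility check at V3 is needed.

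The documents do not show which wording the sponsor intended. If discretion was intended, the alternative is to correct the Malignancies row of Table 1.4: 1, so that the benefit-risk text does not claim a firmer measure than the protocol applies.

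Either way the cost is one clause of protocol wording. The first option also takes some discretion from the investigator in a rare case, in patients with a serious disease and few alternatives. The SAP needs no change.
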